
**Stopping Intervention & Intent-to-Treat Principle:** Subjects are carefully screened at the start of the study in an effort to minimize the need for medical withdrawal. As noted above, the subject's primary care physician is kept informed throughout the study, and if it is the primary care physician's judgment that the subject should not continue in the study, the subject is withdrawn. We have withdrawn patients in the past for worsening joint arthritis, new cancer diagnosis necessitating treatment, diagnosis of coronary artery disease at the mid-testing period (as patients become capable of more work, previously undiagnosed coronary artery disease may surface), or unexpected injuries (e.g., car accidents). If a subject is unable to complete the full intervention protocol, the last available electrodiagnostic primary outcome measurement will be used for the analysis. In these cases, the primary analyses will be based on intention-to-treat principles (i.e., all randomized subjects will be included in the analyses). Protocol adherence will be treated as a co-variate to control for subject compliance. The primary analyses will be repeated, restricted to subjects who complete the intervention protocol. Analysis of covariance (see above) will be used to compare the responses between the intervention groups. Regression will then be used to determine whether the observed intervention persists using adjustment for baseline covariates and measures of treatment compliance.

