**Sample Size Estimate:** The requisite sample size for the proposed study has been based upon the primary outcome measure endpoints of conduction velocity and amplitude. In our preliminary studies (see Table 2), we present data from peroneal nerve conduction velocity and amplitude for sedentary and aerobic (PoleStriding) exercise study groups. We use this information for the proposed study. However, we have not conducted strength training studies and, as such, have had to estimate values that we believe are realistic outcomes. The table below is an estimate of the conduction velocity findings for the proposed study.

		Isokinetic Strength Training	
		No	Yes
Aerobic Training	No	38 m/s	39 m/s
	Yes	39 m/s	43 m/s

Using these estimates we have computed that the effect size for the aerobic plus isokinetic strength training interaction is 0.36. From this, computations indicate that 17 subjects per group will provide 80% power with analysis of covariance to detect an effect size of that magnitude using a 0.05 alpha level. In terms of conduction amplitude, the following table is an estimate of the findings for the proposed study. Again, data from our preliminary studies are incorporated.

		Isokinetic Strength Training	
		No	Yes
Aerobic Training	No	1.9 mV	1.9 mV
	Yes	2.4 mV	4 mV

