Using these estimates we have calculated the effect size for the aerobic training-by-isokinetic strength training interaction to be 0.25. Subsequently, computations indicate that greater than 20 subjects per group will be needed to provide 80% power with analysis of covariance to detect an effect size of that magnitude using a 0.05 alpha level. Given the variability in electrodiagnostic findings *between* our elderly study subjects, inherent limitations in statistical Power are unavoidable. Smaller sample sizes are calculable using *within* person changes. **However, experience gained from our previous funding cycle clearly demonstrates that some electrodiagnostic measures, such as peroneal motor amplitude responses, markedly and significantly increase with aerobic training in diabetic subjects (Table 2, Preliminary Studies).** We hypothesize a larger effect size with the addition of isokinetic strength training which will yield more Power to these analyses using a subject group size of 20. During our previous funding cycle, four of twenty-one (19%) subjects randomized to longitudinal exercise withdrew from study participation. In anticipation of a similar attrition rate, five additional subjects per group will be enrolled, totaling 100 subjects randomized to the four groups. Delays in recruiting during the last funding period have been addressed and resolved. Using the large established pool of recruits, we respectfully argue that our ability to recruit 100 subjects into this 24-week study over a 4-year period is realistic largely because: (i) the proposed time commitment is considerably less than our previously funded application (6 months vs. 18 months) and (ii) we have established a unique data base of study-qualified subjects from which to recruit.

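### On the plan's own inputs the amplitude interaction needs about 32 per group; the plan says only that more than 20 are needed, then adopts 20, where power is about 60% (about 70% at 25)

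*Combined protocol and SAP*

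**What the plan says.** The Sample Size Estimate, within the Statistical Analysis Plan, opens by naming both endpoints as its basis: "The requisite sample size for the proposed study has been based upon the primary outcome measure endpoints of conduction velocity and amplitude". The Statistical Analysis Plan gives primary interest to the interaction of aerobic and strength training in a 2 x 2 factorial analysis of covariance, with baseline as covariate.

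- **Velocity.** Assumed cell means are 38, 39, 39 and 43 m/s, and the interaction effect size is 0.36. The plan concludes that "17 subjects per group will provide 80% power with analysis of covariance".
- **Amplitude.** Assumed cell means are 1.9, 1.9, 2.4 and 4 mV, and the interaction effect size is 0.25. Here the plan gives no exact number, only that "computations indicate that greater than 20 subjects per group will be needed to provide 80% power".

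It then remarks that "inherent limitations in statistical Power are unavoidable", adds "We hypothesize a larger effect size with the addition of isokinetic strength training which will yield more Power to these analyses", and adopts 20 per group. Citing 19% withdrawal in earlier work, it says that "five additional subjects per group will be enrolled, totaling 100 subjects randomized to the four groups".

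Under Stopping Intervention & Intent-to-Treat Principle, "all randomized subjects will be included in the analyses", and for anyone who does not finish the intervention "the last available electrodiagnostic primary outcome measurement will be used for the analysis".

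**The concern.** The plan states a requirement above 20 for one of the two endpoints that set its size, and then uses 20. The five extra per group are there to replace withdrawals, not to close this gap. Because neither the required number nor the power is given, a reader cannot tell a trivial shortfall from a large one, and the sentence about a larger effect suggests that it will take care of itself.

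What is at stake is how a null amplitude result is read. If the assumed interaction is real and power is 60% to 70%, the trial misses it 30% to 40% of the time. A reader who believes the design had about 80% power could take such a miss as evidence that combining the two forms of training brings no added benefit.

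**Working it through.** **Inputs from the Sample Size Estimate.** Alpha 0.05; target power 80%; effect sizes 0.36 (velocity) and 0.25 (amplitude); 20 per group adopted and 25 randomized; four equal groups. The plan does not name the effect-size index. I read it as Cohen's f, because that reading roughly reproduces the velocity number.

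**Method.** Noncentral F for a 1-df interaction with one covariate: df1 = 1, df2 = 4n − 5, noncentrality λ = 4n·f²/(1 − r²). Here r is the baseline-to-outcome correlation; r = 0 means no variance reduction beyond what f already contains.

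**Step 1: reproduce velocity (f = 0.36, r = 0).**
- n = 16: λ = 64 × 0.1296 = 8.29, power 80.9%.
- n = 17: λ = 68 × 0.1296 = 8.81, power 83.2%.

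The smallest n is 16, against 17 stated. Cohen's adjusted-n convention gives exactly 17 (79.6% at 16, 82.1% at 17). A 3-df omnibus test (23) and alpha 0.10 (13) do not fit.

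**Step 2: the same test for amplitude (f = 0.25, r = 0).**

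| n per group | λ = 4n × 0.0625 | Power |
|---|---|---|
| 20 | 5.00 | 59.8% |
| 25 | 6.25 | 69.7% |
| 31 | 7.75 | 78.9% |
| 32 | 8.00 | 80.1% |

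The requirement is 32. Cohen's convention gives 33, and allowing for rounding of 0.25 (0.245 to 0.255) gives 34 to 31. For comparison, velocity has 88.8% power at 20 and 94.6% at 25.

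**Step 3: what 20 and 25 can detect.** The assumed interaction is (4 − 2.4) − (1.9 − 1.9) = 1.6 mV. In a 2 x 2 design f = (interaction/4)/σ, so σ = 0.4/0.25 = 1.6 mV. The f detectable with 80% power is 0.317 at 20, an interaction of 4 × 1.6 × 0.317 = 2.03 mV. At 25 it is 0.283, or 4 × 1.6 × 0.283 = 1.81 mV. Both exceed the assumed 1.6 mV.

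**Step 4: the larger-effect argument.** The 1.6 mV comes wholly from the combined cell being 4 mV rather than 2.4 mV. If strength training added nothing to aerobic training, the interaction would be (2.4 − 2.4) − (1.9 − 1.9) = 0. The gain from strength training is therefore already inside f = 0.25 and cannot be counted again.

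**Step 5: range for baseline adjustment.** This matters only if f = 0.25 was computed from an unadjusted SD. The values of r are assumptions.

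| r | Power at 20 | Power at 25 | n for 80% |
|---|---|---|---|
| 0 | 59.8% | 69.7% | 32 |
| 0.3 | 63.8% | 73.7% | 30 |
| 0.5 | 72.2% | 81.5% | 25 |
| 0.62 | 80.3% | 88.4% | 20 |

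The break-even r for 80% is about 0.62 at 20 and 0.47 at 25.

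**Step 6: range for carry-forward at 25 (r = 0).** Assume that 20% stop, the SD is unchanged, and stoppers keep a share k of the effect. Then f = 0.25 × (0.8 + 0.2k).
- k = 0: f = 0.200, power 51%.
- k = 0.5: f = 0.225, power 61%.
- k = 1: f = 0.250, power 70%.

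**The case against.** The plan's phrase is literally true of 32, so no stated figure is false, and the plan admits limited power. That stands: the fault is an undisclosed gap and an unsound reason for accepting it, not a wrong sum. But an admission without a number does not let a reader tell 78% from 60%.

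The strongest point is that the inputs are not fully visible. The effect-size index is unnamed, the preliminary SDs are not in the sample size section, and the planned analysis adjusts for baseline. If 0.25 rests on an unadjusted SD, true power is higher; at r = 0.5 it passes 80% with 25 per group. This stands as a limit on what can be said about the trial's actual power. It does not rescue the plan's own calculation. Crediting r = 0.5 in the same way for velocity would need only 12 per group, so the stated 17 does not appear to include such a gain.

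The exact figure could be 33 rather than 32, depending on convention. That is a difference of one against a shortfall of 12. The carry-forward range is also assumed, and the 19% withdrawal comes from an earlier study with an 18-month commitment; the conclusion does not depend on that range.

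Finally, the plan may mean an effect larger than the tabled one. That would be a hope without data behind it, since the plan says no strength-training studies had been done and that the values were estimated.

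**Conclusion.** The concern holds. On the method that approximately reproduces the plan's velocity figure, amplitude needs 32 per group (31 to 34 across rounding and convention). The adopted 20 is 12 short, with power of about 60%. Analysing all 25 randomized gives at most about 70% on that method, so the shortfall from 80% is roughly 10 to 20 percentage points.

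This rests on reading the effect size as Cohen's f, a 1-df test at alpha 0.05, and no variance reduction from baseline beyond what f already contains. Power reaches 80% only if f is unadjusted and the baseline correlation is at least about 0.62 (20 per group) or 0.47 (25 per group), neither of which the plan states. On the same inputs velocity exceeds 80% at the planned size, so the defect is confined to the amplitude claim. It should be fixed.

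**What to change.** In the Sample Size Estimate:

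1. Replace the open-ended amplitude requirement with 32 per group, and state the basis: 1-df interaction test, alpha 0.05, no variance reduction from baseline. If the sponsor's own convention gives 33, state that figure and name the convention.
2. Report amplitude power at 20 completers (about 60%, detectable f about 0.32) and at 25 randomized under intention to treat (about 70% nominal, detectable f about 0.28), beside about 89% and 95% for velocity.
3. Name the effect-size index and say whether 0.25 uses the unadjusted or the baseline-adjusted SD. If unadjusted, give the assumed baseline correlation and the resulting power; for example, r = 0.5 gives about 72% at 20 and 82% at 25.
4. Delete the sentence that expects extra power from adding strength training.

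The cost is low: one figure restated, two or three sentences added and one removed. Enrolment and analysis stay as they are. The stated amplitude power becomes less favourable.
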